17.5.1 Adverse Event Definition

An AE is defined as any untoward medical occurrence in a clinical investigation patient reported on or after the first screening date. A treatment-emergent AE (TEAE) is any untoward medical occurrence in a clinical investigation patient or patient administered a pharmaceutical product on or after the initial administration of study medication. An AE does not necessarily have to have a causal relationship with the treatment. An AE can therefore be any unfavorable and unintended sign (including an abnormal laboratory finding), symptom whether or not related to the medicinal (investigational) product, or disease temporally associated with the use of a medicinal (investigational) product.

The AE may be any of the following:

- a new illness
- worsening of a pre-existing condition
- worsening of a sign or symptom of the condition under treatment or of a concomitant illness
- an effect of the study medication, including comparator
- a combination of 2 or more of these factors.

No causal relationship with the study medication or with the clinical study itself is implied by the use of the term "AE."

Surgical procedures themselves are not AEs; they are therapeutic measures for conditions that require surgery. The condition for which the surgery is required may be an AE. Planned surgical measures permitted by the clinical study protocol and the condition(s) leading to these measures are not AEs.

Adverse events fall into the categories “non-serious” and “serious.”

17.5.2 Serious Adverse Events

The reporting period for serious AEs is the same as for AEs. Serious AEs must be submitted to the Sponsor within 24 hours of their discovery, even if the full information about the event is not yet available. These events should also be reported to the IRB/IEC as needed based on local requirements. Fax SAE forms to the following number:

Serious AE [contact]

Also notify the PPD Medical Monitor at **[contact]**.

17.5.2.1 Serious Adverse Event Definition

An SAE is one that, at any dose, results in any of the following:

- Death
- A life-threatening adverse drug experience
- Inpatient hospitalization or prolongation of existing hospitalization
- A persistent or significant disability/incapacity
- A congenital anomaly/birth defect.

A hospitalization is defined as an inpatient admission lasting 24 hours or more. Visits to urgent care centers and emergency departments that do not result in admission to a hospital for 24 hours will not be considered hospitalizations. Hospitalizations for elective procedures, defined as any procedure that was planned prior to signing of the informed consent will not, in and of themselves, be considered to fulfill criteria for an SAE. For example, for patients on the kidney transplant waiting list prior to signing the ICF who subsequently are hospitalized for a transplant, the hospitalization would be considered elective.

The term “life-threatening” in the definition of “serious” refers to an event in which the patient was at immediate risk of death at the time of the SAE. It does not refer to a SAE that hypothetically might have caused death if it were more severe.

Medical and scientific judgment should be exercised in deciding whether other AEs, such as important medical events that may not be immediately life-threatening or result in death or hospitalization but may jeopardize the patient or may require intervention to prevent one of the other outcomes listed above. These should also usually be considered serious. Examples of such events are intensive treatment in an emergency room or at home for allergic bronchospasm; blood dyscrasias, or convulsions that do not result in hospitalization; or development of drug dependency or drug abuse.

Female patients who become pregnant should be immediately discontinued from the study if they have not yet received Study Drug. If a patient is found to be pregnant after they have received Study Drug, she should discontinue dosing, complete all end-of-study

procedures, and be followed to determine the outcome of the pregnancy. Generally, follow-up will be no longer than 6 to 8 weeks following the estimated delivery date. While pregnancy itself is not considered an AE or SAE, any pregnancy complications or less than a healthy, normal outcome will be recorded as an AE or SAE.

Clarification on the difference in meaning between “severe” and “serious”

The term “severe” is often used to describe the intensity (severity) of a specific event (as in mild, moderate, or severe myocardial infarction); the event itself, however, may be of relatively minor medical significance (such as severe headache). This is not the same as “serious,” which is based on the outcome or action criteria usually associated with events that pose a threat to life or functioning. Seriousness (not severity) serves as a guide for defining regulatory reporting obligations.

17.5.3 Non-Serious Adverse Events

A non-serious AE is any AE not meeting the SAE criteria.

17.5.4 Definition of Relationship to Study Medication

Association or relatedness to the study medication will be graded as either “probably,” “possibly,” or “unlikely.” Determination of relatedness includes:

PROBABLY – The AE:

- follows a reasonable temporal sequence from drug administration;
- abates upon discontinuation of the drug;
- cannot be reasonably explained by the known characteristics of the patient’s clinical state.

POSSIBLY – The AE:

- follows a reasonable temporal sequence from drug administration;
- could have been produced by the patient’s clinical state or by other modes of therapy administered to the patient.

UNLIKELY – The AE:

- does not follow a reasonable temporal sequence from drug administration;
- is readily explained by the patient’s clinical state or by other modes of therapy administered to the patient.

17.5.5 Definition of Severity

All AEs will be graded, if possible, by the Common Terminology Criteria for Adverse Events (CTCAE) version 4.03 [http://evs.nci.nih.gov/ftp1/CTCAE/CTCAE_4.03_2010-06-14_QuickReference_5x7.pdf]. This is also provided in the Study Reference Manual for reference purposes.

The severity of AEs that cannot be graded by the most current version of CTCAE will be categorized as follows:

- **Grade 1** – Transient or mild discomfort; no limitation in activity; no medical intervention/therapy required.

- **Grade 2** – Mild to moderate limitation in activity, some assistance may be needed; no or minimal medical intervention/therapy required.
- **Grade 3** – Marked limitation in activity, some assistance usually required; medical intervention/therapy required hospitalizations possible.
- **Grade 4** – Extreme limitation in activity, significant assistance required; significant medical intervention/therapy required hospitalization or hospice care probable.
- **Grade 5** – Death.

17.5.6 Definition of Unexpected Adverse Event

Any AE, the specificity or severity of which is not consistent with the current Investigator's Brochure, rather than from the perspective of such experience not being anticipated from the pharmacological properties of the drug.

17.6 DATA SAFETY MONITORING BOARD

An unblinded, independent Data Safety Monitoring Board (DSMB) will periodically review safety data during the time period that the blinded nalbuphine HCl program remains ongoing. The frequency of data review and DSMB processes are outlined in the DSMB charter. The DSMB will periodically review group-unblinded study information (on a treatment group level, using random letters instead of actual treatments) during the conduct of the study. If necessary, un-blinding of individual subject data and treatment groups may be done.

18 EMERGENCY PROCEDURES

In case of study-related medical questions, or if a pregnancy is confirmed in a trial patient, the Investigator should contact the designated Medical Monitor.

19 CONSIDERATION, ANALYSIS PLAN AND DETERMINATION OF SAMPLE SIZE

19.1 GENERAL

As a companion to this protocol and in an effort to provide a more detailed explanation of the statistical methodology to be used for this study, which will consist of data summaries, a statistical analysis plan (SAP) will be developed prior to locking the data base.

No formal statistical testing is planned for this study. Data summaries will provide the basis for clinical interpretation of efficacy and safety outcomes

19.2 INTERIM ANALYSES

There is no interim analysis planned in this study.

19.3 METHODS FOR HANDLING MISSING DATA

No replacement or imputation of missing data will be conducted for this study.

19.4 PATIENT DISPOSITION

Patient disposition will be summarized, including the reasons for discontinuation. The number of patients in each analysis population will be displayed and an accounting of exclusions from each study population will be provided.

19.5 BASELINE CHARACTERISTICS

Demographics, medical history, laboratory data, and physical examination findings will be summarized.

19.6 CONCOMITANT MEDICATIONS

Concomitant medications will be tabulated by Anatomic and Therapeutic Class (ATC) of WHO drug, preferred term, and treatment group. A medication's usage will be considered concomitant if it was used by the patient at the time of informed consent or started and/or continued after administration of the study medication. If the start date is missing, it will be assumed that the medication was used concomitantly. Rescue and opioid medication usage will be tabulated separately from all other concomitant medications.

19.7 STUDY DRUG DOSING

The percentage of patients reaching various achieved doses at the end of Treatment Week 4 and through Study Week 50 will be summarized. The mean dose during the Treatment Period and the dose distribution by Treatment Period Visit will be reported. Descriptive statistics will be used to describe the mean daily dose by Visit.

19.8 EFFICACY ANALYSES

19.8.1 Efficacy Population

The Safety population, consisting of all enrolled patients who have received a single dose of study medication, will be used to evaluate the efficacy endpoints defined for this study. Eligibility for analysis of a particular endpoint will require only that the patient have a baseline value and at least one post-baseline value for the endpoint of interest, so that a change from baseline calculation can be obtained. All efficacy endpoints will be evaluated through the generation of descriptive summary statistics. For continuous variables, the mean, standard deviation, median, minimum, and maximum will be presented for a particular visit and for the change from baseline (Visit 1a or 1b). For categorical variables, the number and percentage of patients within each category of classification will be summarized by study visit. No formal statistical testing will be conducted.

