9 STUDY PLAN

9.1 GENERAL STUDY DESIGN

This is an open label extension study for patients who have completed the TR03 study.

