9.5 STUDY OVERVIEW

This is an open label safety and tolerability extension study for patients who have completed study TR03. Patients will either enter directly into the drug Treatment Period (Worst Itch NRS greater than or equal to 5 (≥ 5)) or enter an extended screening period of a no-drug Observation Period (Worst Itch NRS less than 5 (<5)) based on their reported NRS scores on the first Visit (Visit 1a). For up to 12 extended screening weeks, patients in the no-drug Observation Period may also transition into the drug Treatment Period if their Worst Itch NRS increases to greater than or equal to 5 (≥ 5).

The total study duration for any individual patient will be up to 53 weeks. For patients who enter directly into the Treatment Period, the total amount of time on drug will not exceed 50 weeks. For patients who enter the Treatment Period from the Observation Period, the total amount of time spent in the combined two periods of the study cannot exceed 50 weeks. All patients who received drug treatment will have a 2-week Washout and Safety Follow-up period at the end of the dosing period, unless consent is withdrawn.

The total amount of time in the Observation Period cannot exceed 12 weeks. After 12 extended screening weeks, patients not eligible for the Treatment Period are screen failed from the study. The study periods are summarized below in [Table 2](#).

Table 2: TR03ext Study Periods

Study Period	Study Weeks	Duration
Observation Period	
Patients who do not meet the criteria to start Treatment are followed in Observation Period visits for up to 12 extended screening weeks. During this time, the patient may meet criteria and become eligible to enter the Treatment Period. If the patient does not meet the criteria to enter the Treatment Period by the end of 12 extended screening weeks (OV12), participation in the study ends and the patient is screen failed.
	Up to 12 extended screening weeks

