9.6.2.2.1 TV 3 (Treatment Week 5)

The following procedures are to take place at this visit:

- complete PAS
- administer the Worst Itch NRS (paper version) and evaluate against the Failure-to-Improve criteria (see [Section 11.1](#))

For patients who MEET the Failure-to Improve criteria:

- Stop study medication
- Perform End of Treatment Visit (TV14) procedures

For patients who DO NOT meet Failure-to-Improve criteria, perform the following procedures:

- obtain vital signs
- collect urine for pregnancy test (regardless of sexual activity) and confirm negative status prior to dispensing additional study drug
- collect blood for PK
- perform 12-Lead ECG after at least 5 minutes in a supine position (See the Study Reference Manual for ECG procedures, [Section 17.4](#) Electrocardiograms for the handling of Cardiovascular adverse events)
- perform brief neurological assessment
- administer PRO measurements (paper versions):
 - Average itch intensity NRS
 - VRS
 - ItchyQoL
 - MOS Sleep-R
 - HADS

The PRO questionnaires must be administered at the study site under the supervision of and by trained study staff, strictly adhering to PRO Administration Instructions (see Study Reference Manual).

- record AEs
- review of concomitant medications, including over-the-counter medications, nutritional supplements, and vitamins
- reinforce and record patient's compliance with dosing and all other required study procedures (i.e. rescue medication log, dosing diary, etc.)
- perform study drug accountability, retrieve previously dispensed study drug
- dispense enough study drug to the patient for required dosing until their next Treatment Visit

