11 PREMATURE DISCONTINUATION OF STUDY DRUG TREATMENT

Patients who complete Study Drug treatment through the End of Treatment Visit (TV14) are considered to have completed Study Drug treatment (even if some doses have been missed). Patients who discontinue Study Drug treatment, **for reasons other than withdrawal of consent**, prior to the End of Treatment visit (TV14) will be considered to have prematurely discontinued Study Drug treatment and will be asked to complete the following visits:

- End of Treatment Visit (TV14) *regardless of where they are in the study visit schedule
- Washout and Safety Follow-up Period Visit
- Premature Discontinuation of Study Drug Telephone Contact Visit

11.1 PREMATURE DISCONTINUATION OF STUDY DRUG TREATMENT ASSOCIATED WITH FAILURE-TO-IMPROVE CRITERIA

Patients, who meet failure-to-improve criteria during the conduct of the study, will stop taking study medication. The Failure-to-Improve criteria are as follows:

Beginning on TV 3, and at every subsequent Treatment Visit, patients with a Worst Itch NRS equal to or greater than (\geq) the Worst Itch NRS at Visit 1a (or at Visit 1b in the case of patients who require the Observation Visit period) will be discontinued from study drug. Patients discontinued from study drug are to undergo the End of Treatment Visit (TV14), the Washout/Safety Follow-up Period assessment in two weeks, and receive a follow-up Telephone Contact 30 days following end of study drug dosing for final safety assessment.

Below are examples of the assessment of Failure to Improve Criteria:

Examples	Visit	Worst Itch NRS	Worst Itch NRS Lower/Higher or no change from V1a/1b	Failure-to-improve met for that visit?	Next Steps
Visit 1a (or Visit 1b)		5	--	--	--
Ex #1	TV3	5	No Change	Yes	Discontinue study drug
Ex #2	TV3	4	Lower	No	Maintain patient on treatment
Ex #3	TV3	6	Higher	Yes	Discontinue study drug

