19.10 DETERMINATION OF SAMPLE SIZE

As this is a safety extension study for which patients will be recruited from patients who have completed parent study TR03, the sample size cannot be predicted. No formal sample size calculations have been performed and no inferential statistics are planned. The maximum number of patients will not exceed the number of patients who completed TR03 (i.e., approximately 60 patients).

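### By-visit efficacy means cover only patients whom the failure-to-improve rule has not yet removed, so they drift towards apparent benefit; they need a conditional label and an all-dosed summary beside them

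*Protocol*

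**What the plan says.** The study is single-arm: "This is an open label extension study for patients who have completed the TR03 study" (Section 9.1). Patients are dosed when Worst Itch NRS reaches 5 at Visit 1a or 1b, and that same reading is the baseline (Sections 5.2 and 9.5).

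The removal rule in Section 11.1 reads "Beginning on TV 3, and at every subsequent Treatment Visit, patients with a Worst Itch NRS equal to or greater than" the baseline value, after which drug is stopped. A stopped patient attends TV14, the washout visit and a telephone contact, but no further Treatment Visits. Table 6 places the check at TV3 to TV13, which is 11 looks.

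At TV3 Worst Itch is taken first. The list with average itch, VRS, ItchyQoL, MOS Sleep-R and HADS then opens with "For patients who DO NOT meet Failure-to-Improve criteria, perform the following procedures" (Section 9.6.2.2.1), and the sections for TV4 to TV13 follow the same pattern. Patients who fail do the TV14 procedures instead, and these include the same questionnaires (Section 9.6.2.2.12).

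For analysis, Section 19.8.1 gives by-visit summaries: "the mean, standard deviation, median, minimum, and maximum will be presented for a particular visit and for the change from baseline". Section 19.3 adds: "No replacement or imputation of missing data will be conducted for this study". Change by Treatment Period visit is a listed secondary endpoint (Section 5.2). Section 4.2 also asks for change by the final Treatment Period Visit.

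**The concern.** The rule that ends follow-up on treatment uses the same variable, Worst Itch NRS, that is then averaged. Anyone contributing a Worst Itch value at TV4 or later has had a negative change at every earlier check. Each further check removes more patients with poor readings, so the mean of those left moves down even if nobody's underlying itch has changed.

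The other patient-reported outcomes carry one more layer of selection. If a stopped patient's questionnaires go into the TV14 row, the TV3 to TV13 rows contain only patients who passed on that same day.

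A final-visit summary that pools stopped patients errs the other way, because their last on-treatment reading is the bad one that stopped them. A drug with no effect could then show clear benefit on one planned summary and slight worsening on another, for the same measure. Section 19.1 makes these summaries the basis for clinical interpretation of efficacy, and nothing in the protocol qualifies the by-visit means for the rule.

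**Working it through.** The plan states no sample size calculation, alpha, power or expected effect ("No formal sample size calculations have been performed and no inferential statistics are planned", Section 19.10), so there is no planned figure to reproduce. The check asks what the planned means would show for a drug that does nothing.

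**Inputs from the protocol.** Integer NRS 0 to 10 (Section 9.7.7.1); entry at 5 or more, with that reading as baseline; removal at the first of TV3 to TV13 with change of 0 or more; no imputation; a ceiling of about 60 patients (Section 19.10).

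**Inputs assumed.** The protocol gives no mean, SD or within-patient correlation for Worst Itch in this population. The scenarios used (mean, SD) before the entry cut of (7, 2), (8, 1.5) and (6, 2.3); correlation between visits of 0.3, 0.5, 0.7 and 0.9; and compound symmetry or AR(1). That makes 3 × 4 × 2 = 24 scenarios, with no other dropout. The nearest figures in the protocol are a median average-itch NRS of 8 in a cited cohort (Section 3.1.1) and a daytime VAS SD of 2.3 in TR01 (Section 3.3.2).

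**Quantities.** Let d(k) be the NRS at TVk minus baseline. A patient attends TVk only if d(j) < 0 at every check j from TV3 up to the visit before TVk.
- No removal: mean of d(k) over everyone.
- Observed, failing readings kept in the row: mean of d(k) over attenders.
- Observed, passers only: mean of d(k) over attenders with d(k) < 0. Applied to Worst Itch, this is the selection that the other questionnaires undergo if failing patients are filed under TV14.

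**Central case, zero effect** (mean 7, SD 2, compound symmetry, correlation 0.5), scaled to 60 patients:

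| Visit | Attending | No removal | Observed, failing readings kept | Passers only |
|---|---|---|---|---|
| TV3 | 60 | -0.21 | -0.21 | -1.94 |
| TV4 | 25.6 | -0.21 | -0.98 | -2.11 |
| TV6 | 10.5 | -0.21 | -1.64 | -2.34 |
| TV8 | 6.1 | -0.21 | -1.99 | -2.51 |
| TV13 | 2.8 | -0.21 | -2.43 | -2.76 |

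The TV3 row shows the mechanism. The 25.6 who pass average -1.94, so the 34.4 who fail average (60 × -0.21 + 25.6 × 1.94) / 34.4 = (-12.6 + 49.7) / 34.4 = about +1.1, and they leave. By TV13 the excess over no removal is -2.43 + 0.21 = -2.22 points, with 2.8/60 = about 5% still attending.

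**All 24 scenarios, zero effect, TV13.**
- No removal: -0.01 to -1.00. This is regression to the mean from using the qualifying score as baseline.
- Observed: -1.2 to -3.5 with failing readings kept, -1.3 to -4.0 among passers.
- Attending: about 1 to 8 of 60.
- The mean fell from TV3 to TV13 in every scenario.
- Last on-treatment value of all patients: +0.07 to +0.90 (central case +0.72).

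A re-run of the 24 scenarios gave the same ranges for the by-visit means and the numbers attending.

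**With a real effect.** A 1.5-point effect gave observed TV13 means of -2.0 to -3.9, against -1.5 to -2.1 had everyone stayed. A 3-point effect with correlation 0.9 and compound symmetry gave -3.04 against -2.99, so the bias almost disappears.

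**The case against.** The strongest case against has four parts.

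- **Efficacy is secondary.** The primary endpoint is adverse events, and efficacy is descriptive and untested, so no decision rule or error rate depends on these means. This stands and limits the severity.
- **The attrition is already reported.** Frequency and timing of failure-to-improve is itself a secondary endpoint (Section 5.2). Disposition and discontinuation for lack of efficacy are also tabulated (Sections 19.4 and 19.8.2). A reader of those tables would see a null drug losing nearly everyone. This stands too, but the tables reveal the loss without correcting the means.
- **Scope.** Worst Itch at TV2 precedes the rule, and at TV3 it is unselected if failing readings stay in that row. The other questionnaires of stopped patients are collected as TV14 procedures, so their selection at the visit depends on visit mapping, which the analysis plan could settle. The point is worded accordingly.
- **Size.** The protocol gives no within-patient variability, so any single figure is an assumption.

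A reader might infer that the by-visit results cannot be interpreted whatever the drug does. The documents do not support that: the removal tables are planned, and the bias is small when the effect is large and scores are stable.

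A reader might also infer that a mixed model should become the headline because the missingness is at random by design. That holds only for rule-driven stops given recorded Worst Itch. Section 11.2 lists other reasons for stopping, and the other questionnaires go missing because of Worst Itch, so a model for them would have to carry it. The result also depends on the covariance. A random-intercept model fitted to AR(1) data with correlation 0.9 and no effect gave -1.65 against a true -0.48, whereas likelihood estimation recovered the truth within 0.07 in 36 other scenarios, AR(1) included. With 60 patients and no effect, the TV13 model estimate had an SD of about 1.1, and about 9% of simulated trials had nobody left at TV13. Such a model also estimates itch had non-improvers continued drug, which the protocol does not set as an objective.

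**Conclusion.** The concern holds and should be fixed; it does not threaten the study's primary purpose. The selection and its direction follow from Sections 11.1, 19.3 and 19.8.1 alone. For Worst Itch it starts at TV4. For the other patient-reported outcomes it starts at TV3 if stop-visit data are filed under TV14. With no effect, the TV13 mean change would read about -1.2 to -4.0, against -0.01 to -1.0 had everyone stayed, on roughly 1 to 8 of 60 patients. The size depends on the assumed means, SDs and correlations and on no other dropout, so it should be quoted only as a range. The pooled final-visit summary is no substitute, since it is pushed the opposite way.

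**What to change.** Amend Section 19.8.1, and leave the stopping rule unchanged.

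1. Assign assessments made when a patient is stopped at TVk to TVk. This includes the triggering Worst Itch reading and the questionnaires done as TV14 procedures. It removes the same-day selection of the other outcomes and needs no new data.
2. Beside every by-visit mean, show n and the cumulative percentage removed. Make the main by-visit efficacy summary the percentage of all dosed patients due at that visit who are on treatment and improved, with a 95% CI, counting removed patients as not improved. This defines an outcome and imputes no score, so it is compatible with Section 19.3. The words due at that visit matter because Table 8 ends treatment visits at TV11 or TV12 for some patients who enter from the Observation Period. In the central null case this percentage falls from 25.6/60 = 43% at TV3 to under 5% at TV13, while the mean appears to improve.
3. Label the by-visit means as conditional on not having met the rule at an earlier visit.

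Optionally, add as a sensitivity analysis a likelihood-based repeated-measures model on all observed Worst Itch NRS, with a prespecified covariance structure that allows serial correlation, and state that its missing-at-random basis covers only rule-driven stops.

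The cost is one mapping rule, one extra table and less favourable late-visit figures. The percentage can also fall for an effective drug, because one reading at or above baseline ends treatment, and without a control arm it does not isolate a drug effect.
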